### 3.2 Safety analysis set (SAF)

The safety analysis set (SAF) comprises all randomized **mothers** who receive at least one dose of the study vaccine or placebo.

### 3.3 Maternal Immunogenicity Set (MIG)

Maternal Immunogenicity Set (MIG) contains the subset of SAF (**mothers**) who receive at least one dose of the study vaccine or placebo and provide an evaluable sample for analysis on any day following first exposure to study vaccine.

### 3.4 Maternal Per Protocol Set (MPP)

Maternal Per Protocol Set (MPP) is the subset of MIG (**mothers**) who receive all doses of the study vaccine or placebo and provide evaluable samples for analysis on the day of the primary immunological endpoint and do not violate the protocol (no major protocol violation/deviation) up to and including the day of delivery.

### **3.5 Baby safety set (BSA)**

Baby safety set (BSA) contains the **babies** born to mothers who have received at least one dose of the study vaccine or placebo (i.e., mothers who belong in the SAF). Note that the number of babies in the BSA could be smaller than the number of mothers in the SAF.

### **3.6 Baby Immunogenicity Set (BIG)**

Baby Immunogenicity Set (BIG) contains the babies born to SAF mothers where the baby provides evaluable samples for analysis, either cord or venous blood, within 72 hours of birth. Note that there need not be a 1:1 correspondence between the MIG and BIG.

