**Footnotes**

- a. Gestational age and gender.
- b. Apgar score at 1, 5 and 10 minutes if available (available scores will be collected, 'not recorded' will be an option).
- c. Heart rate (actual, not Apgar score).
- d. Cord blood or infant blood (heel prick or venous sample) within 72 hours of birth.
- e. Heel prick or venous sample.
- f. Age-appropriate developmental milestone check.
- g. After the first 28 days of age, only MAAEs, AEs of special interest (AESI), e.g., GBS disease and abnormal development according to developmental milestones, or SAEs, and CMs prescribed for such events until 180 days of age.
- h. Visit 9-11 may be performed as home visits.

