## VISITS FOR BABIES:

### Visit 8, Delivery:

The following will be undertaken, and results recorded:

Demography, gestational history (gestational age and gender), physical examination\*, head circumference, length, weight, Apgar score (Apgar score at 1, 5 and 10 minutes, available scores will be collected, ‘not recorded’ will be an option), vital signs (heart rate), immunogenicity cord blood sample (or infant blood sample – heel prick or venous, within 72 hours of birth, if cord blood sample not possible, for target blood volumes for babies see Section 4.4), and AE and CM check.

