#### **4.3.4 Immunogenicity assessments**

In this study the immunogenicity assessments are both related to the study participants (the mothers) and to their babies. In the mothers, pre-specified vaccine induced immune response markers are measured, whereas in the babies, the same immune markers, obtained through passive transport from the mothers to the babies, are measured.

Quantitative ELISAs are used for detection of IgG specific to the AlpN proteins (RibN, Alp1N, Alp2/3N or AlpCN) and IgG specific to the vaccine fusion proteins (GBS-NN and GBS-NN2) in serum samples, using a calibrated reference standard produced from pooled selected sera from previous studies with GBS-NN and GBS-NN/NN2 which contains IgG specific to the individual AlpN domains and the fusion proteins.

In the primary immunogenicity analysis, concentrations of IgG antibodies, specific to the AlpN proteins from cord blood samples taken at delivery/birth are evaluated and compared between the groups, through calculations of geometric mean concentrations and proportions of subjects with IgG concentrations above the pre-defined thresholds.

The secondary immunogenicity measurements of IgG from maternal blood samples taken at 4 weeks after each vaccination and at delivery are evaluated and compared, including calculation and evaluation of ratios of IgG antibody concentrations between maternal and cord/baby blood at delivery.

IgG measurements from infant blood samples taken at 28 days and 3 months of age, are used for calculation of geometric mean concentrations and proportions of babies with IgG concentrations above pre-defined thresholds as part of the secondary immunogenicity analysis.

A large rectangular area of the page is completely blacked out, indicating redacted content. The redaction is bounded by a thin yellow border.

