## 7.6 Analysis populations

Each subject will be classified according to the definitions below at the database release meeting. The classification and related decisions will be made by the study team and documented in the minutes from the meeting. The BIG and BPP sets refer to the children born to study participants.

- Safety analysis set (SAF): All recruited and randomized mothers who receive at least one dose of the study vaccine or placebo
- Maternal Immunogenicity Set (MIG): The subset of SAF who receive at least one dose of the study vaccine or placebo and provide an evaluable sample for analysis on any day following first exposure to study vaccine
- Maternal Per Protocol Set (MPP): The subset of MIG who receive all doses of the study vaccine or placebo and provide evaluable samples for analysis on the day of the primary immunological endpoint and do not violate the protocol up to delivery (no major protocol violation)
- Baby safety set (BSA): The babies born to mothers who have received at least one dose of the study vaccine or placebo
- Baby Immunogenicity Set (BIG): The babies born to mothers who qualify as members of the MIG analysis set
- Baby Per Protocol Set (BPP): The subset of BIG born to MPP mothers where the baby provides evaluable samples for analysis, either cord or venous blood within 72 hrs of birth

All safety analyses will be performed on the SAF and analysed according to actual treatment received (treatment arms 1 to 5). All Immunological analyses will be performed on the MIG and BIG sets. The primary immunological analysis (i.e., the immunogenicity results at delivery) will also be performed on the MPP and BPP sets. These analyses will be based on randomised treatment.

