## 4.6 Analysis of immunogenicity (secondary endpoints)

The following secondary immunogenicity endpoints will be evaluated by standard tabulation by vaccination group and relevant time-point(s):

Based on samples collected in the mother (MIG analysis set):

- Concentrations of IgG antibodies specific to the 4 AlpN proteins in maternal blood, pre-dosing, 4 weeks after each vaccination dose and at delivery
- Relative to baseline (pre-dose) concentrations of IgG antibodies specific to the 4 AlpN proteins in maternal blood, pre-dosing, 4 weeks after each vaccination dose and at delivery

The proportions of mothers who achieve a concentration of IgG specific to the 4 AlpN proteins above 0.1, 0.2, 0.5, 1, 2, 4 and 8 µg/mL at delivery

Based on samples collected in the mother (MIG analysis set) and in the baby (BIG analysis set), and as a sensitivity analysis based on subjects part of the BPP and MPP analysis sets. A further sensitivity analysis will be done on the BPP and MPP, in which biologically implausible data will be eliminated. Examples of such biological implausible data are (non exhaustive list):

- Data from babies born to mothers with a high concentration of antibodies at delivery, where the baby blood at birth shows no or a very low concentration of antibodies, but who show a high concentration of antibodies at later timepoints
- Data from babies born to mothers with a high concentration of antibodies at delivery, where the baby blood shows no or a very low concentration of IgG antibodies, but where IgG1 is detected at the same timepoints, as part of an exploratory analysis

Setting of the elimination of biologically implausible data will be done after review of the initial immunogenicity data output.

- The subject level ratios of antibody concentrations between maternal and cord blood at delivery. The ratio of interest is the antibody concentration measured in cord blood over the antibody concentration measured in maternal blood at delivery. The endpoint is derived for the individual mother-child pair.

Based on samples collected in the baby (BIG analysis set):

- Concentrations of IgG antibodies specific to the AlpN proteins in infant blood of each baby at 1 month and 3 months of age:
- The proportions of babies who achieve a concentration of IgG specific to the AlpN proteins above 0.1, 0.2, 0.5, 1, 2, 4 and 8 µg/mL at 1 month and 3 months after birth will be calculated

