## 7 Deviations from protocol

- An exploratory analysis of weight of infant over time is added.
- Adverse events in babies are added as secondary safety endpoint(s).
- Central monitoring is described in some detail, but no specific analysis of monitoring data is defined.

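### The SAP's baby immunogenicity set requires a birth sample but is also used for infant IgG at 1 and 3 months, so valid later samples can be dropped; the change is not listed as a deviation

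*SAP*

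**What the plan says.** **Definition of BIG.** Protocol section 7.6: "The babies born to mothers who qualify as members of the MIG analysis set". The requirement for cord or venous blood within 72 hours appears there only in the per-protocol set (BPP). SAP section 3.6: "babies born to SAF mothers where the baby provides evaluable samples for analysis, either cord or venous blood, within 72 hours of birth". The SAP thus moves the requirement into BIG and replaces MIG mothers with SAF mothers.

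**Use of BIG.** The introduction to SAP section 3 places all immunological analyses on MIG and BIG. SAP section 4.6 introduces infant IgG at 1 and 3 months with "Based on samples collected in the baby (BIG analysis set" and names no other set. SAP section 3.1 notes that set membership can be settled from information up to 72 hours after delivery.

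**Purpose of the later samples.** Protocol section 4.3.4: "IgG measurements from infant blood samples taken at 28 days and 3 months of age, are used for calculation of geometric mean concentrations", together with proportions above thresholds. Protocol Table 3, footnote e, accepts a "heel prick or venous sample" at those visits.

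**Declared deviations.** SAP section 7 has three entries: the infant weight analysis, baby adverse events ("Adverse events in babies are added as secondary safety endpoint(s") and central monitoring. BIG is not mentioned.

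**Birth sample type.** Protocol Table 3, footnote d: "Cord blood or infant blood (heel prick or venous sample) within 72 hours of birth". The baby Visit 8 description in protocol section 4.3.2 accepts infant blood by "heel prick or venous, within 72 hours of birth, if cord blood sample not possible". Protocol section 3.5, BPP in both documents, and SAP sections 1.1.2.1, 3.6 and 4.5 name venous blood as the only substitute for cord blood.

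**The concern.** A set defined by a sample at birth is being used for endpoints measured one and three months later. The later samples are drawn at separate visits and do not depend on whether cord blood was obtained. As written, the 1- and 3-month geometric means and threshold proportions describe only babies whose birth sampling succeeded. That discards usable data and selects babies on an event unrelated to the endpoint. Because section 7 does not list the change, a reader comparing the results with the protocol would not be told that the set had been redefined.

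A related point touches the primary endpoint. The documents allow a heel-prick sample at birth but do not name it in the endpoint or set definitions, so it is unclear whether a newborn with only a heel-prick sample counts.

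**Working it through.** **The plan's own figure.** The only design figure is power above 90% at the 1 µg/mL cut-point with 60 per group. Exact binomial enumeration of the rule (lower limit of the 90% Newcombe-Wilson interval above -0.15, true rate 22/23 = 95.65% in both groups, n = 60) gives 96.7%, so the statement is reproduced. It concerns the birth endpoint. With no imputation, a baby without a birth sample contributes nothing there under either definition, so the figure does not bear on this point.

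**Definitions side by side.**

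| | Protocol BIG | SAP BIG |
|---|---|---|
| Mothers | MIG | SAF |
| Baby's birth sample | no condition | cord or venous, within 72 hours |
| Used for 1- and 3-month IgG | yes (section 7.9) | yes (section 4.6) |
| Listed in SAP section 7 | n/a | no |

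A baby of a MIG mother with evaluable samples at Visits 9 and 10 but no cord or venous sample at birth is in the protocol's BIG and outside the SAP's. The same holds for a baby sampled by heel prick throughout, although heel prick is acceptable at the later visits. Under SAP section 3.1, a later valid sample does not bring the baby back in.

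**Size.** The documents give no rate of missing or non-qualifying birth samples, so I assume a fraction f of 0% to 15%. The losses are upper bounds, since some of these babies would also lack later samples.

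- Babies lost: 270 × f and, per vaccine group, 60 × f. Placebo: 30 × f.
- Relative interval width, taking width as proportional to 1/√n: 1/√(1 − f).
- Wilson 95% interval at an observed 50%: the width simplifies to z/√(n + z²), with z = 1.96 and z² = 3.84.

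| f | Lost of 270 | Lost of 60 | Lost of 30 | Relative width | Wilson width, 60-baby group |
|---|---|---|---|---|---|
| 0% | 0 | 0 | 0 | 1.000 | 1.96/√63.84 = 24.5 points |
| 5% | 13.5 | 3 | 1.5 | 1/√0.95 = 1.026 | n = 57: 1.96/√60.84 = 25.1 points |
| 15% | 40.5 | 9 | 4.5 | 1/√0.85 = 1.085 | n = 51: 1.96/√54.84 = 26.5 points |

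**Related wording conflicts.**

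- *Birth sample type.* Heel prick is allowed in footnote d of Table 3 in both documents, in the protocol's baby Visit 8 description and in protocol section 4.4, where it ranks third. It is absent from protocol section 3.5, BPP in both documents, and SAP sections 1.1.2.1, 3.6 and 4.5. The conflict already exists within the protocol.
- *Time window.* SAP Table 3, footnote d, says 48 hours; protocol footnote d and the SAP endpoint and set text say 72.
- *Maternal visits.* SAP Table 5 gives Visits 1, 4, 6 and 7 for IgG four weeks after each dose. Protocol Table 2 has immunogenicity samples at Visits 1, 3, 5, 7 and 8, matching the five counted in protocol Table 4. Two of the four visits in that row, 4 and 6, therefore have no IgG sample. The model in SAP section 4.6 uses Visits 3, 5, 7 and 8, and SAP section 6 refers the early analysis to section 4, so this is an error in the table.

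**The case against.** The strongest reply is that little is at stake. The endpoints are secondary and tabulated without hypothesis tests, all data are still listed, attrition is expected to be low, and sampling staff are blinded, so nothing suggests that missing birth samples would differ by group. All of this stands and limits the weight of the point. Listings do not, however, replace the geometric means and proportions that the protocol names as endpoints, and expected low attrition gives no rate for failed birth samples.

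A second reply is that a single baby set suits a description of decline over time. But SAP BIG does not require later samples, so it does not produce a constant cohort.

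Third, moving from MIG to SAF can also add babies, so the net change from the protocol's set may be smaller than the losses shown. That is true, and the net change cannot be computed. The figures bound the loss relative to the set proposed below, which also starts from SAF mothers.

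Fourth, the Wilson method is assigned only to the birth proportions, and 50% is my choice. The widths are therefore illustrative.

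Fifth, permission to collect a heel-prick sample is not an eligibility rule, and the set text consistently says cord or venous. That is a fair reading of the SAP. Even so, the protocol's Visit 8 text lets heel prick stand in for cord blood, and its own BIG sets no sample type, so the two documents together do not settle the matter.

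Finally, section 3.6 states its definition openly, and the protocol requires deviations to be described in the study report. The missing section 7 entry is a documentation gap, not concealment.

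**Conclusion.** The concern holds. Followed as written, the SAP removes valid 1- and 3-month samples from named secondary endpoints when the birth sample is missing or of the wrong type, and section 7 declares neither change to BIG.

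The consequence is modest: some loss of precision and a selection on birth sampling, in descriptive tables. Under the assumed 0% to 15% range, the loss runs from nothing to at most about 41 of 270 babies, with intervals at most 8.5% wider. The true rate is unknown and no direction of bias is claimed. The stated power is unaffected, and the added condition does not itself remove primary-endpoint data. The heel-prick ambiguity is the one element that reaches the primary endpoint. The 48-hour footnote and the Table 5 visits are clerical.

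**What to change.** 1. Analyse the 1- and 3-month endpoints in all babies of SAF mothers with an evaluable sample at the visit concerned. Keep the birth-sample condition for the birth endpoint only.
2. Add both BIG changes (birth sample required; MIG replaced by SAF) to SAP section 7.
3. State one list of acceptable birth sample types and one time window in footnote d of Table 3, the sampling text, the endpoint text, BIG and BPP. Either name heel prick in the endpoint and set definitions or remove it from the birth-sample provisions. Retain the cord-only sensitivity analysis in SAP section 4.5 as the check.
4. Correct the SAP Table 5 row to Visits 1, 3, 5 and 7.

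The visit-specific set, the section 7 entry, the 48-hour footnote and the Table 5 row need SAP wording only. The heel-prick rule also requires protocol sections 3.5 and 7.6 to be aligned, by a protocol clarification or a listed SAP deviation. No new data collection is needed. The price is that the number of babies analysed will vary by time point and must be shown in every table.

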### **3.7 Baby Per Protocol Set (BPP)**

Baby Per Protocol Set (BPP) contains the subset of BIG (babies) born to MPP mothers where the baby provides evaluable samples for analysis, either cord or venous blood within 72 hrs of birth.

Note that the BPP will be smaller or equal to the MPP (in size).

## 4 Statistical analyses and presentation of data

### 4.1 General considerations and summary of analyses

Summary tables presenting immunogenicity data (mothers and babies alike) as well as AEs including solicited injection site events and systemic AEs following the vaccinations will be presented a) pooled across all countries/sites and b) by geographical location South Africa / Europe (DK+UK).

All data collected from all sites will be sent to and analysed at Larix. Unless otherwise specified, all statistical tests will be performed using a two-sided test at a 5% significance level. Results from analyses will be presented with estimates, 95% confidence intervals (CIs) and p-values. For log-transformed analyses, which might be relevant for immunogenicity endpoints, the anti-log transformation will be applied before presentation. These transformed data will also be tabulated by geometric mean and coefficient of variation. Exposure to vaccinations and compliance with the vaccination schedule will be tabulated and listed.

Numerical/continuous data will be presented in summary tables by number of subjects, arithmetic mean (geometric mean and coefficient of variation [CV] where applicable), median, standard deviation (SD), minimum and maximum (or range). Categorical data will be presented by frequency and percent of subjects as well as number of events, where applicable. All data will be listed (see section 9, Layout of the outputs), and all endpoint data will be tabulated.

As there are more than one observation per subject (both mothers and babies) over time, time-dependent visualizations and, if possible, corresponding time-dependent statistical tests and modelling are carried out.

Prior and concomitant medication will be coded after WHO Drug Dictionary. Medical history and adverse events will be coded using the latest available version of MedDRA.

### 4.2 Data imputations

As the main principle, data will be analysed as collected and no imputation performed.

#### Adverse events

Missing causality, intensity, seriousness, and outcome of an adverse event (AE) will not be imputed in summary reporting.

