#### **Reasonable possibility of being related**

An event for which, after careful medical evaluation, a connection with trial medication cannot be ruled out with certainty. The event occurs after exposure to trial medication. The event may occur at a reasonable time in relation to the time of administration of the trial medication but might also be attributable to a commonly occurring alternative cause. Alternatively, the event may not occur at a reasonable time in relation to the time of administration of trial medication but may not be attributable to an alternative cause.

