### Adverse Reaction:

An AE assessed as related (reasonable possibility of being related) to the investigational product administration. All injection site events are defined as related to the investigational product.

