## 6.4 Reporting of adverse events including SAEs, MAAEs and AESIs

AEs will be reported in the eCRF pages from informed consent until the subject has completed/is withdrawn from the study (including any follow-up period), see details in Table 2 for mothers and Table 3 for babies.

Adverse events identified from the e-diaries will be transferred to the AE form in the eCRF, if they meet the following criteria:

- Any unsolicited AE
- Solicited local or systemic reaction to be assessed for the subject's withdrawal from study or study vaccine
- Solicited local or systemic reaction, rated by the subjects in the eDiary, categorized as severe
- Solicited local or systemic reaction lasting beyond 7 days from the day of vaccination
- Solicited local or systemic reaction that meets the definition of a SAE

Solicited local or systemic reactions are per definition regarded as related to the study vaccine, and the intensity is defined as described in section 6.1.

All maternal SAEs, as well as medically attended adverse events (MAAEs) and AEs of special interest (e.g., GBS disease, autoimmune diseases and immune-mediated reactions) will be reported from the day of signing informed consent for study participation and until the end of the study (Visit 11).

All baby SAEs, as well as MAAEs and AESIs (e.g., GBS disease, abnormal development according to developmental milestones), will be reported from birth up to 180 days post-delivery (Visit 11).

All SAEs, and AESIs, occurring from the time of signing the informed consent form until the subject has completed the study will be reported by completing and sending the SAE form (via email, or if required, via fax) to the pharmacovigilance provider (contact details below) within 24 hours of awareness / learning about the event i.e., within 24 hours after the investigator becomes aware that the event meets the protocol definition of a SAE.

SAEs occurring after study termination must be reported if considered related to the study drug.

After the initial SAE report, the investigator is required, proactively, to provide further information regarding the subject's condition.

In case of a fatal or life-threatening suspected unexpected serious adverse reaction (SUSAR), relevant follow-up information should be forwarded immediately.

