#### Adverse events and concomitant medication dates

If the start date of an AE is incomplete, a full start date will be imputed following a ‘worst case’ logic favouring treatment emergency and length of AE duration. If the incomplete start date is unambiguously before date of first vaccination, the latest possible date compatible with the partial date, but before first vaccination, will be chosen. Otherwise, the earliest possible date compatible with the partial date, but after date of first vaccination will be chosen. So, for example:

Completely missing start date:

- the AE will be considered as concomitant/treatment emergent with the start date imputed as treatment start date.

If Month is missing:

- If the incomplete date is in the same year as day of first dosing, assign the treatment start date as the AE/medication start date.
- If this is not the case, assign January as the month and the 1.th of January as day/month if AE/medication day is also missing.

If Year is missing:

- Impute the year of first vaccination. If the imputed date is then after first vaccination date then retain it. Otherwise impute the date of first vaccination.

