## 4.7 Analysis of safety (key secondary endpoint)

### 4.7.1 Adverse events

AEs relating to mothers (study subjects) will be coded using the latest available version of MedDRA. An overall summary table will be provided showing the number and percentage of subjects, within the SAF analysis set, with any:

- Treatment-emergent adverse events (TEAEs)
- Severe TEAEs
- Vaccine related TEAEs
- Vaccine related severe TEAEs
- Treatment-emergent SAE
- Treatment-emergent vaccine related SAEs
- TEAEs leading to withdrawal
- TEAEs with outcome death

The frequencies of the following key secondary safety endpoints will be tabulated in descriptive frequency tables:

- Treatment-emergent solicited injection site reactions
- Treatment-emergent solicited systemic AEs
- All treatment-emergent AEs
- For solicited events and reactions the summary tables will furthermore be presented by vaccination number/visit.

Treatment emergent AEs will be tabulated by system organ class and preferred term and treatment using the latest MedDRA coding.

All treatment emergent events will be listed. Non-treatment emergent events (if any) will be listed separately.

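### TEAEs with missing causality or intensity cannot count in the vaccine-related and severe rows of the safety summary, so those rows can only be understated

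*SAP*

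**What the plan says.** The general rule in SAP 4.2 is: "As the main principle, data will be analysed as collected and no imputation performed". For adverse events it adds: "Missing causality, intensity, seriousness, and outcome of an adverse event (AE) will not be imputed in summary reporting".

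The next part of SAP 4.2 treats incomplete AE start dates differently: "a full start date will be imputed following a ‘worst case’ logic favouring treatment emergency and length of AE duration".

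SAP 4.7.1 plans an overall table of the number and percentage of women in the safety set with various kinds of TEAE. Four rows depend on causality, intensity or both: severe TEAEs, vaccine-related TEAEs, "Vaccine related severe TEAEs" and vaccine-related SAEs. The section gives no category for missing values and no sensitivity row. It also plans separate tables of solicited reactions, overall and by vaccination number, and a listing of all TEAEs. SAP 4.7.2 carries the same approach over to babies.

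The protocol fixes causality for two kinds of event. Section 6.1: "All injection site events are defined as related to the investigational product". Section 6.4: "Solicited local or systemic reactions are per definition regarded as related to the study vaccine". The SAP repeats neither definition.

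**The concern.** A blank field satisfies neither 'related' nor 'severe'. With no imputation and no missing category, an event with that field blank adds nothing to the rows that depend on it. Compared with complete assessment, those rows can be too low but never too high.

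The rows report key secondary safety results in pregnant women. Protocol 2.5 says that the safety results, together with cord-blood immunogenicity, inform the choice of regimen for phase III. The rarest rows are the most sensitive, because one unassessed event can be the difference between none and one.

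The SAP gives no reason for being conservative about dates and the opposite about causality and intensity. An event with both start date and causality missing is placed among the TEAEs by the date rule and then cannot count among the vaccine-related TEAEs.

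**Working it through.** The documents give no AE rate and no rate of missing causality or intensity, so there is no planned figure to reproduce. The check has a textual part and an arithmetical part.

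**1. What happens to each kind of event under the text as written**

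| Event | Field blank | Documents' position | Effect on the table |
|---|---|---|---|
| Injection-site event or solicited reaction | Causality | Related by definition (Protocol 6.1, 6.4); not restated in SAP | Should count as related; at risk only if the SAP is programmed without the definition |
| Any other TEAE | Causality | Not imputed (SAP 4.2) | Cannot count in the three vaccine-related rows |
| Any TEAE | Intensity | Not imputed (SAP 4.2); the protocol definitions above concern relatedness only | Cannot count in the two severe rows |

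In every case the event stays in the any-TEAE row and in the listing. A woman is missed from a row only if she has no other event that qualifies for it.

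The first line of the table matters because of which solicited reactions reach the AE form. Under Protocol 6.4 these include the severe ones, those lasting beyond 7 days, those meeting the SAE definition and those to be assessed for withdrawal. They are natural contributors to the related-and-severe and related-and-serious rows.

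**2. Sensitivity of a row**

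Inputs: 60 women in each of Groups 1 to 4 and 30 in Group 5 (Protocol 4.2, Table 1). If *m* women are missed out of *N*, the row is low by 100 × *m*/*N* percentage points.

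- Active group: 100 × 1/60 = 1.7 points for one woman; 100 × 3/60 = 5.0 points for three.
- Placebo group: 100 × 1/30 = 3.3 points for one woman; 100 × 3/30 = 10.0 points for three.
- All active groups together: 100 × 1/240 = 0.4 points for one woman.

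**3. A rare row**

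For zero events the exact (Clopper-Pearson) two-sided 95% upper limit is 1 − 0.025^(1/*N*). For one event it comes from the same exact method.

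- *N* = 60: 0 events gives 1 − 0.025^(1/60) = 6.0%; 1 event gives 8.9%.
- *N* = 240: 0 events gives 1 − 0.025^(1/240) = 1.5%; 1 event gives 2.3%.

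This shows what one event is worth. SAP 4.7.1 itself plans only numbers and percentages for these rows.

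**4. Illustration under assumed rates**

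Assume that a share *r* of women truly have a related TEAE not covered by the protocol definitions, and that in a share *b* of them causality is blank on the only such event. The row is then low by *r* × *b*.

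- Low end, *r* = 10% and *b* = 2%: 0.10 × 0.02 = 0.2 points, or 60 × 0.002 = 0.12 women per group of 60.
- High end, *r* = 30% and *b* = 10%: 0.30 × 0.10 = 3.0 points, or 60 × 0.03 = 1.8 women per group of 60.

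Both ranges are assumptions.

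**The case against.** The strongest case on the other side is that this is a small clarification.

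- **No conflict with the protocol.** A reader might infer that SAP 4.2 contradicts Protocol 6.1 and 6.4. It does not. Where relatedness follows from a definition, setting it is a derivation, and SAP 4.2 bars only imputation. The SAP presents itself as an elaboration of the protocol, and its section 7 lists no departure from these definitions. What stands is an omission. The definitions are also silent on intensity, which for solicited reactions comes from the eDiary records and the grading scale in Protocol 6.1.
- **Unassessed is not the same as related.** A reader might argue that Protocol 6.1 already makes an unassessed event related, because it covers events where "a connection with trial medication cannot be ruled out with certainty". That clause presupposes that a medical evaluation has been made. An event nobody has assessed falls outside it, so counting it as related is a conservative convention and not a reading of the protocol.
- **Events are not lost.** They remain in the any-TEAE row and the listings, and solicited reactions have their own tables, which do not depend on causality. The table shells are a separate document (SAP 10) and could contain a missing row. This limits the effect. It does not settle the matter in the SAP, where the rule belongs.
- **Blanks may be few, especially for serious events.** Protocol 7.2 provides for checks on incomplete data, Protocol 6.4 requires SAE forms within 24 hours with active follow-up, and SAP 5 tracks related SAEs and related grade 3 events close to real time. This is a fair reason to expect a small effect in the rare rows.
- **Dates are different.** A start date decides whether an event is treatment-emergent at all, so a separate rule for dates is not an inconsistency in logic. The point stands only as a difference in direction: one rule is conservative and the other is not.
- **Coding every blank as severe goes too far.** An event blank in both fields would become a vaccine-related severe TEAE with no investigator's judgement behind it. This is accepted, and the fix treats intensity differently from causality.

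**Conclusion.** The point holds as a cheap improvement to the safety tables. SAP 4.2 and 4.7.1 together leave the vaccine-related and severe rows open to a downward error with no disclosure of its extent. The size is 1.7 points per affected woman in an active group and 3.3 points in placebo. The total is unknown because the documents give no rate of missing fields; under the assumed ranges above it is between 0.2 and 3.0 points for the vaccine-related row.

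The conclusion assumes that the separate table shells do not already add a missing category, that some blanks survive data queries, and that some affected women have no other qualifying event.

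A reader might also infer that the rule would distort the comparison between regimens. The documents do not support that: safety assessors are blinded (Protocol 4.2), and nothing suggests that blanks would be more frequent in one group than another.

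**What to change.** Replace the sentence on missing AE attributes in SAP 4.2, as far as it concerns causality and intensity, with three rules for summary tables:

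1. Injection-site events and solicited reactions are set to related, as Protocol 6.1 and 6.4 define.
2. Any other TEAE whose causality is still missing after query resolution is counted as related. A footnote gives the number assigned this way in each arm.
3. TEAEs with missing intensity appear in a separate missing category. A worst-case row that counts them as severe is shown as a sensitivity display.

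Listings keep the values as missing. Rules 2 and 3 should also be applied to the baby AE tables under SAP 4.7.2.

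The cost is one SAP paragraph, a derived flag and one extra row per affected table. The related percentages, and the severe percentages in the worst-case row, may be slightly less favourable. The related rows may include events without an investigator's causality judgement, which the footnote discloses.
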